6.1.4. ISI

The ISI is a seven-item instrument that quantifies the participant perception of insomnia severity, along with the impact of insomnia on daytime functioning in adults in the last two weeks (Bastien et al. 2001). The seven questions are with respect to:

- difficulty falling asleep
- difficulty staying asleep
- problems waking up too early
- satisfaction/dissatisfaction with current sleep pattern
- noticeability of sleep problems by others
- worries/distress caused by the sleep difficulties
- extent of interference of sleep difficulties with daily functioning.

It is scored on a five-point Likert scale from 0 to 4 depending on the item:

- Items 1-3: 0='none' to 4='very severe'
- Item 4: 0='very satisfied' to 4='very dissatisfied'
- Item 5: 0='not at all noticeable' to 4='very much noticeable'

version 3.0 Page: 64 of 87

- Item 6: 0='not at all worried' to 4='very much worried'
- Item 7: 0='not at all interfering' to 4='very much interfering' (Item 7)

The scores for each item are summed to produce the total score (maximum 28) which allow categorization of severity of insomnia.

Total score categories:

- 0-7 = No clinically significant insomnia
- 8–14 = Subthreshold insomnia
- 15–21 = Clinical insomnia (moderate severity)
- 22–28 = Clinical insomnia (severe)

6.1.5. EQ-5D-5L

The EQ-5D-5L is a self-administered preference-based generic measure of health status which includes five dimensions (EQ-5D-5L User guide):

- 1. mobility
- 2. self-care
- 3. usual activities
- 4. pain/discomfort
- 5. anxiety/depression.

Participants provide a rating for each question on a five-point Likert scale:

- for items 1-3: no problems, slight problems, moderate problems, severe problems, unable to do
- for item 4: no pain, slight pain, moderate pain, severe pain, extreme pain
- for item 5: not anxious or depressed, slightly anxious or depressed, moderately anxious or depressed, severely anxious or depressed, extremely anxious or depressed.

In addition, participants are asked to self-rate their own health today on a vertical 0-100 unit visual analogue scale (VAS), with 0 corresponding to "the worst health you can imagine", and 100 corresponding to "the best health you can imagine".

6.1.6. Short Form-36 Health Survey Acute (SF-36 acute)

The SF-36 acute is a widely used measure of general health status with well-documented reliability, validity, and responsiveness in the general population as well as in various disease indications. It consists of 36 items which are responded to using item specific 1-5 or 1-3 Likert scales. The acute version has a recall period of 1 week. The items are comprising 8 domains: physical function, role physical, bodily pain, general health, vitality, social functioning, role of emotional and mental health and two composite scores, the physical component score (PCS) and mental component score (MCS). Scores from individual items of each subscale are combined to form a subscale rating and are transformed to a 0 to 100 scale. Higher scores indicate better quality of life.

version 3.0 Page: 65 of 87

Descriptive analysis will base on the single item level assessment, aggregation of single item scores to the 8 health domains respectively, and calculations: the psychometrically-based physical component summary (PCS) and the mental component summary (MCS) scores. Transformed and calculated scores are provided by external Vendor.

6.1.7. **BDI-II**

The BDI-II consists of 21 items to assess the severity of depression over the past 2 weeks (Beck et al. 1996). The 21 items are with respect to various symptoms of depression, specifically:

- Sadness
- Pessimism
- Past Failure
- Loss of Pleasure
- Guilty Feelings
- Punishment Feelings
- Self-Dislike
- Self-Criticalness
- Suicidal Thoughts or Wishes
- Crying
- Agitation
- Loss of Interest
- Indecisiveness
- Worthlessness
- Loss of Energy
- Changes in Sleeping Pattern
- Irritability
- Changes in Appetite
- Concentration Difficulty
- Tiredness or Fatigue
- Loss of Interest in Sex

Each item consists of a list of four response options arranged in increasing levels of severity, except for "Changes in Sleeping Pattern" and "Changes in Appetite" which contain 7 response options each. For the items with 4 response options, each item is rated on a 4-point verbal response scale ranging from 0 (not at all) to 3 (extreme form of each symptom). The items with 7 response options are also scored from 0 to 3 as

version 3.0 Page: 66 of 87

Response option $1 \rightarrow \text{score}=0$

Response option 2 or $3 \rightarrow \text{score}=1$

Response option 4 or $5 \rightarrow \text{score}=2$

Response option 6 or $7 \rightarrow \text{score}=3$.

The total score ranging from 0 to 63 is calculated by summing up the ratings to the 21 items.

6.2. Appendix 2: Pattern-mixture modeling approach for supplementary analysis

A pattern mixture modeling approach (Little, 1993) will be used in combination with multiple imputation (Ratitch, O'Kelly et al., 2013; Wang et al. 2023) to handle missing and unobservable data that occur in presence of ICEs in a way that aligns with the estimand strategy for each type of ICE.

We will use a reference-based pattern imputation approach which makes use of observed data from the reference group for estimating the multiple imputation model for each pattern that requires distinct assumptions about a plausible distribution of missing/unobservable data. The reference group consists of participants who are expected to have similar outcomes to those with missing/unobservable values after conditioning on baseline covariates and, in some cases, partially observed data. Pattern definitions and the corresponding reference groups that will be used for the supplementary analysis of the primary and key secondary endpoints are specified in Table 4–5 and Table 4–7.

The pattern-mixture multiple imputation and analysis method will be implemented by a series of steps using SAS PROC MI, MIXED, and MIANALYZE:

1. Imputation: Impute missing and unobservable values at baseline, Week 1, 4, 8 and 12 (see Table 4–5 and Table 4–7 for definition of patterns):

Impute intermittent (non-monotone) missing values that occur outside of the time frame of any ICE as well as missing and unobservable values that occur in presence of ICEs in pattern 1.

A joint multivariate normal multiple imputation model will include outcomes at baseline, Week 1, 4, 8 and 12, as well as the fixed, categorical effects of treatment and stratification factor (type of treatment of pre-existing condition at baseline). This step will be implemented using PROC MI with the MCMC statement and the following options: "CHAIN = MULTIPLE" and "SEED = 21656" to produce 500 imputed datasets. The input dataset will contain all participants with missing/unobservable data targeted by this step as described above and participants from the reference group, i.e., participants who complied with the randomized treatment (please see the definition of compliance in Table 1–2). Partially imputed data will serve as input to complete imputation in patterns 3 and 4.

version 3.0 Page: 67 of 87

Impute missing values occurring during an ICE associated with pattern 2.

A multiple imputation regression model will be used to model change from a time point before treatment interruption to a time point during treatment interruption as the dependent variable (change equal to pre-interruption value minus value at the time point of interruption). The model will include as predictors the baseline value, value before treatment interruption, and the fixed, categorical effects of treatment and stratification factor (type of treatment of pre-existing condition at baseline). Because the number of participants in this pattern is expected to be small, modeling of change in outcome from pre-interruption to during interruption will be done by pooling data across time points where treatment interruptions occur. Missing values at a time point k will be replaced by adding the change value predicted by the imputation model to the participant's value at the time point (k-1) prior to treatment interruption. This step will be implemented with PROC MI and MONOTONE REG statement explicitly specifying the model described above. The input dataset will include all participants in pattern 2 and participants with temporary interruption due to treatment unrelated reasons from pattern 1 who have observed data before and during the interruption.

Impute missing and unobservable data occurring during an ICE associated with pattern 3.

Missing values that occur after the ICE in pattern 3 will be imputed using a similar MI model as used in the main analysis of the primary endpoint as described in Section 4.2.1, that is, the wash-out method (Wang, et al. 2023).

Impute missing and unobservable data occurring during an ICE associated with pattern 4.

If there are any intermittently missing data in this pattern, they will be imputed using PROC MI with the MCMC statement and "CHAIN = MULTIPLE" option to perform partial imputation and obtain a monotone missing pattern. The remaining monotone unobservable data in this pattern will be imputed using multiple imputation regression models for outcome at each affected time point. The model will include as predictors the baseline value, values at time points before treatment discontinuation, and the fixed, categorical effects of treatment and stratification factor (type of treatment for pre-existing condition). The input dataset will include all participants in the analyses set, their observed values and values imputed on previous steps outlined above. That is, the MI model for pattern 4 will reflect a mixture of participants, some of which fully comply with the randomized treatment and some with other types of ICEs.

If an unobserved/missing value is imputed below 0, a post processing step will be applied to set the imputed value 0.

In order to impute a missing value at baseline (as part of the imputation of intermittent missing values), a minimum of 2 post-baseline values (out of 4) should have been observed for the participant.

version 3.0 Page: 68 of 87

At the end of the four imputation steps, 500 datasets will be produced and each imputed dataset will be analyzed as described in the analysis step below.

2. Analysis: Estimate of the treatment difference based on each imputed dataset, using the analysis model for the primary endpoints (i.e. MMRM as specified in Section 4.2.1).

The estimated treatment difference at Week 4 and 12 from all imputed datasets will be saved and combined in the next step as described below.

3. Combining results of analyses from multiple imputed datasets: The results of the MMRM analysis on 500 imputed datasets will be combined using Rubin's rule to derive the final estimate for the treatment difference, its 95% CI and p-value (one-sided). This will be done using SAS PROC MIANALYZE.

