4.1.2. Data Rules

Definition of baseline: The latest available valid measurement excluding unscheduled measurements at or before the start of treatment (for treated subjects) / randomization date (for randomized but not treated subjects). If the last observation available prior to randomization is the measurement from the Screening Visit, this would be used as the baseline value. In case a wash-out period was necessary, measurements taken during the prescreening visit will not be used as a baseline value unless specified otherwise.

Change from baseline: To calculate the absolute change from baseline the baseline value will be subtracted from the value under treatment/follow-up, i.e.,

Absolute change = post baseline value – baseline value.

Some parameters will be additionally analyzed as relative change defined as

Relative change = 100 * [(post baseline value – baseline value) / baseline value].

Derivation of intercurrent event (ICE): Intercurrent events that occurred from randomization date (for randomized but not treated subjects) / start of treatment (for treated subjects) to day 84 inclusive will be flagged.

version 3.0 Page: 24 of 87

For the "permanent discontinuation of randomized drug", "intake of prohibited medication having impact on efficacy" and "interruption/ discontinuation in intake of adjuvant endocrine therapy", if the ICE occurs on or before the 5th day of the week, it will be flagged for the respective week. If the ICE occurs on the 6th or 7th day of the week, it will be flagged from the following week. For example, if the participant permanently discontinues from the randomized drug on the 2nd day of week 4, the ICE will be flagged from week 4 onwards. If the discontinuation from the randomized drug occurs on the 6th day of week 4, then the ICE will be flagged from week 5 onwards. For the ICEs "intake of prohibited medication having impact on efficacy" and "interruption/ discontinuation in intake of adjuvant endocrine therapy", if the end date for the impact on efficacy occurs on the 1st or 2nd day of the week, the respective week should not be flagged. If the end date of impact on efficacy occurs on or after the 3rd day of the week, the week should be flagged.

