1	Intake of prohibited medications Any reason	Hypothetical strategy If participant did not take prohibited concomitant medication. Discard the collected data after the intake of prohibited medication(s) for a certain time frame based on the medication class (See Section 6.4.2 for details).	Participants, from the same arm, who comply with treatment regimen ^b and have observed data at the time point that requires imputation.
	Temporary treatment interruption ^a	Hypothetical strategy If participant complied with treatment.	
	Due to COVID-19/ administrative or any other treatment unrelated reasons	Data collected for a specific assessment during/after a temporary treatment interruption will be discarded for that assessment Week only.	

version 3.0 Page: 37 of 87

2	Temporary treatment interruption ^a Due to AE	Treatment policy strategy Utilize all the collected data in the analysis.	Participants, from the same arm, who have available data before and during the treatment interruption. MI will be used to model change from a time point before treatment interruption to a time point with treatment interruption (Copy Increment from Reference imputation
3	Permanent treatment discontinuation	Treatment policy/Hypothetical strategy	Missing values that occur after the ICE will be imputed using a similar MI
	Due to AE/lack of efficacy	If participant remained untreated/on background therapy after permanent discontinuation of the randomized treatment, use the treatment policy strategy and utilize the collected data.	model as used in the main analysis of the primary endpoint, i.e., the wash-out method (Wang et al. 2023).
		Otherwise, if participant initiated an alternative treatment, use the hypothetical strategy under the hypothetical scenario "If participant did not initiate an alternative treatment after permanent discontinuation of randomized treatment". Discard data after the ICE.	
4	Permanent treatment discontinuation Due to COVID-19/ administrative or any other treatment unrelated reasons	Hypothetical strategy If participant did not discontinue the randomized treatment due to the specified reason. Any data collected after permanent treatment discontinuation will be discarded.	All other participants from the same arm (i.e., participants without a similar ICE at the time point that requires imputation).
	Interruption/Discontinuat ion in intake of adjuvant endocrine therapy	Hypothetical strategy If participant did not stop adjuvant endocrine therapy	

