1	Temporary treatment interruption ^a Due to COVID-19 /administrative or any other treatment unrelated reasons	Hypothetical strategy If participant complied with treatment. Data collected for a specific assessment during/after a temporary treatment interruption will be discarded for that assessment Week only.	Participants, from the same arm, who comply ^b with treatment regimen and have observed data at the time point that requires imputation. (same as the first supplementary analysis)
2	Temporary treatment interruption Due to AE	Treatment policy strategy Utilize all the collected data in the analysis.	Participants, from the same arm, within the same pattern who have available data before and during the treatment interruption. MI will be used to model change from a time point before treatment interruption to a time point

version 3.0 Page: 42 of 87

			with treatment interruption (Copy Increment from Reference imputation strategy). (same as the first supplementary analysis)
3	Permanent treatment discontinuation (Due to AE/lack of efficacy)	If participant remained untreated/on background therapy after permanent discontinuation of the randomized treatment, use the treatment policy strategy and utilize the collected data.	Missing values that occur after the ICE will be imputed using a similar MI model as used in the main analysis of the primary endpoint, i.e., ,the wash-out method (Wang et al. 2023) (same as the first supplementary analysis)
		Otherwise, if participant initiated an alternative treatment, use the composite strategy assuming treatment failure (i.e. no change from baseline). Discard data after the ICE and assign the value of zero change from baseline	N/A
4	Permanent treatment discontinuation. Due to COVID-19 /administrative or any other treatment unrelated reasons	Hypothetical strategy If participant did not discontinue the randomized treatment due to the specified reason. Any data collected after permanent treatment discontinuation will be discarded.	All other participants from the same arm (i.e., participants without a similar ICE at the time point that requires imputation). (same as the first supplementary analysis)

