6.4. Appendix 4: Details regarding the identification of intercurrent events

6.4.1. Temporary treatment interruption

Per definition (see Section 1.1), the ICE "temporary treatment interruption" will only be considered for week 1, week 3 and 4, week 7 and 8, and week 11 and 12. Specifically, temporary treatment interruption is defined as

- Treatment taken on <5/7 days during week 1 for Week 1
- Treatment taken <80% during weeks 1-4 OR treatment taken on <5/7 days during either week 3 or 4 for Week 4

version 3.0 Page: 69 of 87

- Treatment taken <80% during weeks 1-8 OR treatment taken on <5/7 days during either week 7 or 8 for Week 8
- Treatment taken <80% during weeks 1-12 OR treatment taken on <5/7 days during either week 11 or 12 for Week 12.

The criterion for treatment taken on 5/7 days during the corresponding two weeks, as defined above, is met, if in any selected 7 consecutive days within those weeks, the treatment has been taken for less than 5 days (i.e., at least 3 missed intakes).

If the criterion is met, an ICE flag will be placed for the corresponding visit week for HFDD. For PROMIS and MenQoL, the ICE flag will be placed only if the questionnaire is filled in after the third drug missed intake day.

To identify whether < 80 % treatment was taken, planned compliance during weeks 1-4 will be calculated as

100 * Number of capsules taken / 56

where 56 is based on two tablets per day over 28 days. Planned compliance during weeks 1-8 will be calculated as

100 * Number of capsules taken / 112

where 112 is based on two capsules per day over 56 days.

Planned compliance during weeks 1-12 will be calculated as

100 * Number of capsules taken / 168

where 168 is based on two capsules per day over 84 days.

To calculate the number of days per week with treatment intake, a day where at least one capsule was taken, will be considered as a day with treatment intake.

For the identification of the ICE temporary treatment interruption, the compliance and daily treatment intake will be calculated based on the ePRO instrument 'Study drug intake documentation'.

Regarding the reasons, AEs that lead to a treatment interruption, together with start and end date, will be collected on the respective eCRF page. Similarly, reasons related to COVID-19 or administrative reasons will also be collected in the eCRF.

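### SAP Section 6.2, pattern 2: change is defined as before minus during but then added to the before value, so the imputed change has the wrong sign

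*SAP*

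**What the plan says.** SAP Section 6.2 (Appendix 2) sets out four imputation patterns for the two supplementary estimands. Pattern 2 covers values missing during a temporary interruption caused by an adverse event.

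- **Dependent variable, in words:** "change from a time point before treatment interruption to a time point during treatment interruption as the dependent variable".
- **Dependent variable, as a formula:** the parenthesis that follows reads "change equal to pre-interruption value minus value at the time point of interruption".
- **Filling the gap:** "Missing values at a time point k will be replaced by adding the change value predicted by the imputation model" to the participant's own value at time point k−1, before the interruption.
- **Predictors:** baseline value, value before the interruption, treatment and type of endocrine therapy. Data are pooled over time points: "Because the number of participants in this pattern is expected to be small".

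Table 4–5 (Section 4.2.3.1) describes the same step as "MI will be used to model change from a time point before treatment interruption to a time point with treatment interruption" and names the method Copy Increment from Reference. Table 4–7 (Section 4.2.3.2) repeats this for the second supplementary estimand. For change from baseline, Section 4.1.2 says "the baseline value will be subtracted from the value under treatment/follow-up", that is, later minus earlier.

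**The concern.** Either sign convention works if it is used throughout. This text uses one to define the change and the other to apply it, so the increment taken from the reference participants is applied backwards. If hot flashes rise during an interruption, the rule imputes a fall of the same size, and the reverse.

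Section 6.2 is also the programming specification, since it says PROC MI is to be run with the model as described there. Code that follows it literally is wrong, and validation against the SAP would pass it. Code that silently corrects it departs from the SAP without a record.

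At stake are the two supplementary analyses. They apply to the primary endpoints and, through Section 4.3.1.4, to the key secondary endpoints. Pattern 2 values can also pass into later steps: the input for pattern 4 includes values imputed earlier, and Section 4.2.3.1 says the reference groups for patterns 3 and 4 may contain such participants. The main analysis (Section 4.2.1) and the tipping point analysis (Section 6.3, which reuses the Section 4.2.1 imputation) do not involve pattern 2.

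**Working it through.** **Algebra.** Let Y(k−1) be the value before the interruption and Ŷ(k) the model's prediction during it. Because Y(k−1) is itself a predictor, the predicted change under the SAP definition is D̂ = Y(k−1) − Ŷ(k). The SAP then imputes

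Y(k−1) + D̂ = 2 × Y(k−1) − Ŷ(k).

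The intended value is Ŷ(k). With d = Ŷ(k) − Y(k−1), the error is −2d.

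| Before | Predicted during | Imputed as written | Intended |
|---|---|---|---|
| 5 | 7 | 3 | 7 |
| 5 | 3 | 7 | 3 |
| 4 | 4 | 4 | 4 |
| 3 | 8 | −2, floored to 0 | 8 |

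The floor at 0 in Section 6.2 truncates negative results; it does not correct the sign. A least-squares fit to simulated data with the SAP's predictors gave the same identity to within 1.4 × 10⁻¹⁴.

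**Is the sign reversed elsewhere?** No. The wording in the same sentence, Tables 4–5 and 4–7 and Section 4.1.2 all point to during minus before. The two SAP supplements add safety analyses only.

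**Effect on the treatment difference.** Let p be the share of values in an arm imputed this way at a given week, and let d differ by arm. The shift in elinzanetant minus placebo is about

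−2 × (d_E × p_E − d_P × p_P).

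With 270 and 135 randomized (Section 5), one participant contributes −2/270 = −0.0074 times d on elinzanetant, or +2/135 = +0.0148 times d on placebo.

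The SAP reports no result for this step, and the documents give neither the counts nor d. The cases below are assumed illustrations, not bounds.

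| Assumed case | Shift (hot flashes/day) |
|---|---|
| 5 elinzanetant, d = +2 | −20/270 = −0.074 |
| 5 elinzanetant, d = −2 | +20/270 = +0.074 |
| 3 placebo, d = −2 | −12/135 = −0.089 |
| 4 elinzanetant and 2 placebo, all d = +2 | −16/270 + 8/135 = 0 |
| 4 elinzanetant with d = +2, 2 placebo with d = −2 | −16/270 − 8/135 = −0.119 |

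A simulation of 4,000 trials applied the floor and assumed a baseline mean of 11, a baseline SD of 5 and a residual SD of 1.5 in the increment. It gave −0.068, −0.085, +0.003 and −0.111 for the first, third, fourth and fifth cases, within 0.01 of the formula.

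**Yardstick.** The planned standard error with 243 and 122 evaluable participants is SD × √(1/243 + 1/122) = SD × 0.111. That is 0.403 at Week 4 (SD 3.632) and 0.476 at Week 12 (SD 4.29). In absolute size the five cases are 0.18, 0.18, 0.22, 0 and 0.29 of the Week 4 standard error.

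**The case against.** The strongest reply is that this is a slip inside one parenthesis. The rest of the sentence, both tables and the named method show what was meant, and a programmer who knows Copy Increment from Reference would probably code it correctly. No success criterion depends on the step, few participants are expected, and the largest illustration needs changes of opposite sign in the two arms, which no text supports. All of that is fair. It limits the consequence, but the formula as written still gives the wrong value.

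Narrower points also have some force:

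- **Change convention.** Section 4.1.2 defines change from baseline only. It suggests a convention and does not govern change between two later visits.
- **Endpoints.** For the questionnaires, Section 6.4.1 says "For PROMIS and MenQoL, the ICE flag will be placed only if the questionnaire is filled in after the third drug missed intake day". Read literally, few or no missing PROMIS or MENQOL values would reach pattern 2, leaving mainly hot flash frequency, where a week is missing only if more than 2 days lack data. The sentence may, however, be only a timing rule, and both supplementary estimands formally cover those endpoints.
- **Minimum reference group.** Section 4.2.3.1 stops imputation at an intermediate time point with fewer than 10 reference participants. If counted per arm, 10 is 3.7% of 270 or 7.4% of 135, so the step might not run. Section 6.2 pools over time points and adds interrupted participants from pattern 1, so this is only one reading.
- **Carry-over to pattern 3.** Its wash-out model for elinzanetant is estimated from placebo participants, so only placebo pattern 2 values could enter it, and only if imputed values count as available.
- **Yardstick.** The shifts use 270/135 and the standard error 243/122. On 270/135 the Week 4 standard error is 3.632 × √(1/270 + 1/135) = 0.383, and the largest ratio becomes 0.119/0.383 = 0.31. The conclusion is the same.

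**Conclusion.** The rule is wrong as written. Followed exactly, it reverses every predicted pattern 2 change, with an error of −2d per imputed value. This rests on the SAP text and algebra alone.

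The consequence is confined to missing values during interruptions for adverse events in the two supplementary analyses, plus any carry-over to patterns 3 and 4. It is likely small: at most 0.12 hot flashes a day in the illustrations, which rest on assumed counts and changes of ±2 a day. The direction depends on which arm is affected and on the sign of d, so no bias in favour of either arm is claimed. Whether the program contains the error cannot be told from the documents. It should be fixed, but it does not threaten the confirmatory result.

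**What to change.** In SAP Section 6.2, pattern 2, make one of two equivalent changes:

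1. Define the dependent variable as the value during the interruption minus the value before it, and keep the addition. This matches the rest of the SAP.
2. Keep the present definition and subtract the predicted change.

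Either returns Ŷ(k). Then check that the pattern 2 code uses one sign throughout and record the result. If it does not, rerun both supplementary analyses for every endpoint where pattern 2 values were imputed. The cost is one line of text and a code check. The design, data collection and confirmatory analysis do not change, and I see no downside.
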